4.4. Sample Size Determination

Based on the assumption of targeted primary endpoint response rates of at least 50% in the luspatercept group and 10% for the placebo group, and 2:1 randomization, a total sample size of

150 (100 in the luspatercept group, 50 in the placebo group) will have at least 99% power to detect the difference between the 2 groups with a 2-sided alpha of 0.05 and assumed 10% dropout rate.

For NTDT-PRO T/W domain scores, assume the mean change from baseline scores at Week 24 are 1.2 and 0.5 for luspatercept and placebo group, respectively, with a common standard deviation of 1.2, the statistical power will be 91%.

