8.2. Baseline Characteristics

The following baseline characteristics will be summarized.

- Beta-thalassemia diagnosis: Beta-Thalassemia, Hemoglobin E/Beta-Thalassemia, Beta-Thalassemia combined with Alpha-Thalassemia;
- Baseline hemoglobin level (mean of at least 2 Hb values by central lab at least 1 week apart during the 28 days screening period) summarized as continuous variable as well as by category (≥ 8.5 g/dL and < 8.5 g/dL) excluding the Hb values within 21 days following a transfusion;

- Baseline NTDT-PRO T/W Score (calculated over 7 days prior to Dose 1 Day 1 detailed in Section 18.3.1) summarized as continuous variable as well as by category (≥ 3 points and < 3 points);
- Baseline NTDT-PRO SoB Score (calculated over 7 days prior to Dose 1 Day 1 detailed in Section 18.3.1);
- Baseline transfusion burden in units/24 weeks before Dose 1 Day 1 (descriptive and categorized level: \leq median value and $>$ median value if baseline transfusion burden > 0);
- Baseline transfusion burden in units/12 weeks before Dose 1 Day 1 (descriptive and categorized level: \leq median value and $>$ median value if baseline transfusion burden > 0);
- Beta-thalassemia gene mutation grouping: Beta Allele 1 Mutation, Beta Allele 2 Mutation, Alpha Gene 1 Mutation, Alpha Gene 2 Mutation, Other Disease-related Mutations
- Eastern Cooperative Oncology Group (ECOG) performance status (0 or 1) at screening visit to assess how the disease affects subjects' daily activities: 0 = fully active, able to carry on all pre-disease performance without restriction; 1 = restricted in physically strenuous activity but ambulatory and able to carry out work of a light or sedentary nature, e.g., light housework, office work; A listing will be provided for ECOG data.
- Splenectomy: Yes/No;
- Baseline Serum Ferritin;
- Hepatitis B and C results;
- MRI liver iron content (LIC) (descriptive and categorized level: < 3 , ≥ 3 - ≤ 5 , > 5 - ≤ 7 , > 7 - ≤ 15 and > 15). The value of LIC will be either the value collected from eCRF or the value derived from T2*, R2* or R2 parameter depending on which techniques and software was used for MRI LIC acquisition. Please refer to Section 10.4.10 for more imputation details
- Bone mineral density DXA scan (BMDs and T-scores by location);
- Baseline 6-Minute Walk Test (6MWT);
- Baseline FACIT-F Fatigue Subscale (FS);
- Baseline SF-36 PCS and MCS Scores.

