10.1 Multiplicity

Gate-keeping methods will be used to control the overall Type 1 error rate for the key secondary endpoints. After the result from the primary efficacy analysis in the ITT population shows statistical significance, the key secondary endpoint 1 will be tested next. The key secondary endpoint 2 will be tested only if the test results for both primary endpoint and the key secondary endpoint 1 are significant. The key secondary endpoint 3 will be tested only if the test results for primary endpoint and the key secondary endpoints 1 and 2 are all significant. The testing procedure above will be implemented strictly in order to control the overall Type 1 error rate of 0.05 due to multiplicity.

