10.3 Analyses of Key Secondary Efficacy Endpoints

The analyses of key secondary efficacy endpoints will be performed on the ITT population. The key secondary endpoints will be tested in the order as mentioned from Section 10.1 and listed below:

- 1 Mean change from baseline in NTD-PRO Tiredness and Weakness (T/W) domain score over a continuous 12-week interval from Week 13 to Week 24.
- 2 Mean hemoglobin change from baseline over 12-week interval from Week 13 to 24 during the treatment period in the absence of transfusions.
- 3 Proportion of subjects who have an increase from baseline ≥ 1.0 g/dL in mean of hemoglobin values over a continuous 12-week interval from Week 37 to Week 48 in the absence of transfusions.

To control the overall Type 1 error rate for secondary endpoints, the testing procedure will be implemented strictly in order: the test for key secondary endpoint 1 will only be conducted when there is evidence showing that erythroid response is achieved in the luspatercept group from Week 13 to Week 24 (primary endpoint). The key secondary endpoint 2 will be tested only if the test results for both primary endpoint and the key secondary endpoint 1 are significant. The key secondary endpoint 3 will be tested only if the test results for primary endpoint and the key secondary endpoints 1 and 2 are all significant.

10.3.1 NTD-PRO (T/W Domain) Mean Change Between Weeks 13 to 24

The change from baseline on mean of NTD-PRO (T/W domain) over a 12-week interval between Weeks 13 to 24 will be analyzed using analysis of covariance (ANCOVA) method with treatment group in the model and randomization stratification factor(s) as covariates. Treatment effect will be evaluated as a contrast of luspatercept versus placebo. Least squares (LS) means with

corresponding standard errors (SE) for each treatment group, along with LS mean of treatment difference with corresponding 95% CI and p-value will be presented.

The subgroup analyses including baseline NTDT-PRO T/W (≥ 3 and <3) will be performed as described in Section 10.5.

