The treatment-by-stratification-factor(s) interaction will be added to the ANCOVA model as a sensitivity analysis and results from this model will be compared to the primary fixed effects model (without the interaction effect). If the interaction is significant at a 2-sided 0.1-alpha level, the nature of this interaction will be inspected as to whether it is quantitative (that is, the treatment effect is consistent in direction but not in size of effect) or qualitative (the treatment is beneficial in some values of the stratification factor(s)). If the interaction effect is found to be quantitative, results from the primary fixed effect model will be presented. If the interaction effect is found to be qualitative, further inspection will be used to identify in what values of the stratification factor(s) the treatment is more beneficial.

10.3.2 Hemoglobin Mean Change Between Weeks 13 to 24

Mean Hb change from baseline over a 12-week interval between Weeks 13 to 24 will be analyzed using ANCOVA method with treatment group in the model and randomization stratification factor(s) as covariates. Treatment effect will be evaluated as a contrast of luspatercept versus placebo. Least squares (LS) means with corresponding standard errors (SE) for each treatment group, along with LS mean of treatment difference with corresponding 95% CI and p-value will be presented.

Baseline hemoglobin (Hb) is the average of 2 or more Hb measurements at least 1 week apart within 4 weeks prior to Dose 1 Day 1. The Hb values within 21 days following a transfusion may be influenced by the transfusion and will be excluded from this analysis. For discontinued subjects who do not complete 24 weeks of the DBTP, Hb data will continue to be collected. For a subject, if the Hb average over Weeks 13-24 interval cannot be calculated due to missing data, the closest Hb 12-week average will be used as described in Section 5.1. If the value is still missing, the imputation method will be performed as described in Section 10.6.1.

A waterfall plot will be provided for the hemoglobin change from baseline by treatment group. Individual subject's hemoglobin change from baseline will be displayed in a single bar. The displayed hemoglobin change is each subject's largest decrease in hemoglobin.

The subgroup analyses including mean baseline Hb (≥ 8.5 g/dL and <8.5 g/dL) will be performed, as described in Section 10.5.

10.3.3 Hemoglobin Response Between Weeks 37 to 48

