10.4 Analyses of Other Secondary Efficacy Endpoints

The analyses of other secondary efficacy endpoints will be performed on the ITT population except for the FACIT-F and SF-36 endpoints listed in this section. The analyses of NTDT-PRO, FACIT-F, and SF-36 endpoints will be conducted based on the Health Related QoL evaluable population (Section 5.2.4).

10.4.1 FACIT-F Fatigue Subscale (FS): Mean Change from Baseline between Weeks 13 to 24 and Weeks 37 to 48

Mean FACIT-F FS score change from baseline over a 12-week interval between Weeks 13 to 24 (nominal Dose 5 to Dose 9) will be analyzed using ANCOVA method with treatment group, randomization stratification factor(s) in the model and baseline FACIT-F FS score as covariate. The baseline of FACIT-F FS is the score from the last visit prior to or on Dose 1 Day 1.

Mean change from baseline for Weeks 37 to 48 (nominal Dose 13 to Dose 17) will be analyzed similarly.

The subgroup analyses for Weeks 13-24 will be performed as described in Section 10.5.

10.4.2 NTDT-PRO SoB Score: Mean Change from Baseline between Weeks 13 to 24 and Weeks 37 to 48

Mean NTDT-PRO SoB score change from baseline over a 12-week interval between Weeks 13 to 24 will be analyzed using ANCOVA method with treatment group, randomization stratification factor(s) in the model and baseline NTDT-PRO SoB score as covariate. Similar analysis will be performed for Weeks 37 to 48.

10.4.3 Hemoglobin Mean Change Between Weeks 37 to 48

Mean Hemoglobin change from baseline over 12-week interval between Weeks 37 to 48 during the treatment period will be analyzed using ANCOVA method with treatment group and randomization stratification factor(s) in the model as covariates.

Baseline hemoglobin (Hb) is the average of 2 or more Hb measurements at least 1 week apart within 4 weeks prior to Dose 1 Day 1. The Hb values within 21 days following a transfusion may be influenced by the transfusion and will be excluded from this analysis. For discontinued subjects who do not complete 24 weeks of the DBTP, Hb data will continue to be collected. For a subject, if the Hb average over Weeks 37-48 interval cannot be calculated due to missing data, the closest Hb 12-week average will be used.

10.4.4 NTDI-PRO (T/W Domain) Mean Change Between Weeks 37 to 48

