10.4.18 Longitudinal Analysis of Hemoglobin Mean Change from Baseline

A mixed effect repeated measure model will be used with intercept and time as the random effect to evaluate the hemoglobin change from baseline at Weeks 12, 24, 36 and 48. The model includes the weekly change from baseline up to Week 48, and treatment group assignment, time (weeks since Dose 1 Day 1), baseline hemoglobin, randomization stratification factor(s), time-by-baseline score, and time-by-treatment group assignment terms in the model. The unstructured covariance matrix will be used to obtain the random effects variance components.

If the MMRM model using an unstructured covariance matrix fails to converge with the default Newton-Raphson algorithm, the Fisher scoring algorithm or another appropriate method will be used to provide initial values of the covariance parameters. In the rare event that none of the above methods yields convergence, a structured covariance, such as heterogeneous Toeplitz and Toeplitz structures, will be used to model the correlation among repeated measurements. In this case, the empirical option will be used because the sandwich variance-covariance estimator is asymptotically consistent.

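### The T/W and hemoglobin change models adjust for baseline only through two-level strata; adding the continuous baseline is a near-costless gain in precision

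*SAP*

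**What the plan says.** Randomization is stratified by baseline hemoglobin (cut at 8.5 g/dL) and baseline T/W score (cut at 3 points) (SAP 4.3). In four analyses these two-level factors are the only form in which baseline enters:

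- T/W change, Weeks 13-24 (SAP 10.3.1, key secondary 1): "analysis of covariance (ANCOVA) method with treatment group in the model and randomization stratification factor(s) as covariates".
- Hemoglobin change, Weeks 13-24 (SAP 10.3.2, key secondary 2): "ANCOVA method with treatment group in the model and randomization stratification factor(s) as covariates".
- Hemoglobin and T/W change, Weeks 37-48 (SAP 10.4.3 and 10.4.4): "ANCOVA method with treatment group and randomization stratification factor(s) in the model as covariates".

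Protocol 9.6.2.1, 9.6.2.2, 9.6.3.3 and 9.6.3.4 likewise name no baseline covariate. In 9.6.2.1 and 9.6.2.2 the sentence is also broken: a stray word (score, value) stands where a covariate would be named.

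The other change-from-baseline models keep the strata and add the outcome's continuous baseline: FACIT-F fatigue subscale (10.4.1), shortness of breath (10.4.2), SF-36 (10.4.6), chelation dose (10.4.7), ferritin (10.4.9), LIC (10.4.10) and 6MWT (10.4.14). Shortness of breath is the other domain of the same diary, and its model has "randomization stratification factor(s) in the model and baseline NTDT-PRO SoB score as covariate". The longitudinal hemoglobin model (10.4.18) includes "baseline hemoglobin, randomization stratification factor(s), time-by-baseline score".

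On testing order, SAP 10.1 says that "key secondary endpoint 2 will be tested only if the test results for both primary endpoint and the key secondary endpoint 1 are significant"; key secondary 3 requires all the earlier tests to succeed.

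**The concern.** Cutting a continuous baseline at one point discards information about the outcome. If change is correlated with baseline, a model that holds only the stratum leaves more residual variance than necessary.

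The continuous term is absent exactly where the outcome's own baseline is already a stratification factor, which looks like a rule rather than an oversight. The plan does not apply that rule throughout, however: SAP 10.4.18 carries both baseline hemoglobin and the strata.

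Neither type I error nor the validity of the comparison is at stake. What is at stake is precision on the T/W test. It has the lower of the two stated powers (91%, against at least 99% for the primary endpoint), and failure there stops formal testing of key secondaries 2 and 3. No T/W sensitivity analysis in this SAP adds the continuous baseline. They vary the treatment-by-stratum interaction (10.3.1) or the handling of missing data (10.6.2).

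**Working it through.** **Inputs from the plan (SAP 4.4).** T/W difference 1.2 - 0.5 = 0.7; SD 1.2; 100 and 50 patients; two-sided 0.05; 10% dropout. The T/W analysis is complete-case (SAP 10.6.2), so 90 and 45 patients are used below.

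**Assumed, because the documents do not give them.** Correlation r between baseline and change, 0 to -0.6. Normal baseline T/W with SD 2 and mean 3.0 to 4.2, with 5.0 as a further case. The figure 1.2 is taken as the unadjusted SD of change.

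**Step 1: the plan's figure.** The plan says "with a common standard deviation of 1.2, the statistical power will be 91" percent. At 100/50, SE = 1.2 × √(1/100 + 1/50) = 0.2078 and 0.7/0.2078 = 3.37. Power is 92.0% by normal approximation and 91.7% by noncentral t, which agrees. At 90/45, SE = 0.2191 and the noncentral t gives 88.7%.

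**Step 2: what the stratum keeps.** A cut placing a proportion p above 3 keeps a share c² = φ(z)²/[p(1-p)] of baseline variance. At mean 4.2, z = (3 - 4.2)/2 = -0.6, p = 0.726 and c² = 0.3332²/(0.726 × 0.274) = 0.56. The share is 0.64 at mean 3.0 and 0.44 at mean 5.0.

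**Step 3: residual SD and power.** Strata only: 1.2√(1 - r²c²). With continuous baseline: 1.2√(1 - r²). At r = -0.3 and mean 4.2 these are 1.170 and 1.145. Noncentral-t power at 90/45 and mean 4.2:

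| r | Strata only | Plus baseline |
|---|---|---|
| -0.3 | 90.2% | 91.4% |
| -0.5 | 92.8% | 95.6% |
| -0.6 | 94.4% | 97.7% |

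**Step 4: simulation.** 6,000 trials per setting, 2:1 permuted blocks of 3 within the four strata, both strata in both models. Change in power from adding continuous baseline, means 3.0 to 4.2:

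| r | Change (points) | Example at mean 4.2 |
|---|---|---|
| 0 | -0.1 to -0.4 | |
| -0.2 | +0.1 to +0.3 | |
| -0.3 | +0.8 to +0.9 | 90.1% to 90.9% |
| -0.4 | +1.4 to +2.2 | |
| -0.5 | +1.6 to +2.6 | 92.7% to 95.3% |
| -0.6 | +2.5 to +3.4 | 94.0% to 97.4% |

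At mean 5.0 the gains are +1.1, +3.2 and +4.2 points at -0.3, -0.5 and -0.6. Type I error is unaffected: 5.5% for both models at r = 0, and 4.8% against 4.9% at r = -0.5.

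A separate simulation (10,000 trials, 65% of patients at 3 or above) gave 90.3% to 91.0% at -0.3, 93.0% to 95.4% at -0.5, and a loss from 88.5% to 88.0% at zero.

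**Step 5: equivalent sample size.** This is the squared ratio of mean SEs. At r = -0.3: (0.2124/0.2096)² = 1.027 at mean 3.0 and (0.2134/0.2097)² = 1.036 at mean 4.2. At -0.5: (0.2007/0.1901)² = 1.115 and (0.2030/0.1902)² = 1.139. At -0.6: (0.1917/0.1752)² = 1.197 and (0.1956/0.1757)² = 1.239. That is about 3% to 4%, 11% to 14% and 20% to 24% more patients.

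**Step 6: hemoglobin.** The plan gives no SD. If both arms are normal with equal SD, response rates of 50% and 10% at 1.0 g/dL imply a mean difference of 0 - (-1.28) = 1.28 SD. At 90/45 the strata-only model then has power above 99.99%, and 98.7% if the effect is 40% smaller.

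**The case against.** The strongest reply is that nothing here is wrong. Stratum-only ANCOVA is valid under randomization, the protocol and SAP name the same covariates, and each affected outcome already has its own baseline among the strata. On that reading shortness of breath is a weak comparator, since without the added term its baseline would not be adjusted for at all. SAP 10.4.18 is also thin evidence of policy, because its text closely follows the SF-36 paragraph. All of this is fair, and it keeps the point an improvement rather than an error.

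The size can also be challenged. With baseline SD 2 and change SD 1.2, follow-up variance is 4 + 1.44 + 4.8r, which equals baseline variance at r = -0.30. Reaching -0.5 or -0.6 needs follow-up variance of 3.04 or 2.56, a fall of 24% or 36%. Averaging over 12 weeks could produce some shrinkage, but the documents do not show that much. This stands: about one point is the reasonable expectation under equal variances, and the larger gains are conditional.

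Only T/W at Weeks 13-24 has power at stake. Hemoglobin change has power to spare, and neither Weeks 37-48 change endpoint is in the gated sequence. That also stands. A separate HRQoL SAP, not available here, may include a baseline-adjusted T/W analysis, but the gating test is the one in this SAP.

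Finally, the change would come late. Enrolment was complete when the SAP was written (SAP 16), and Weeks 13-24 diary data had been used to set the responder threshold (SAP 10.4.16). Protocol 13.5 requires ethics approval for amendments that are not administrative. This adds procedure but does not block the change: a blinded SAP revision before lock is enough to fix the model, and the protocol wording can be aligned with it.

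**Conclusion.** The point holds as a matter of efficiency and consistency. Four models use baseline only as a two-level factor, while the rest of the plan uses the continuous value as well. For T/W at Weeks 13-24 the expected gain is about one power point at a correlation of -0.3 and about 1.6 to 3.2 points at -0.5 across the baseline means examined. The loss is at most about half a point if the correlation is zero. These figures rest on an assumed correlation, a normal baseline with SD 2, and 1.2 being the unadjusted SD. Type I error and the plan's 91% are not called into question. For hemoglobin the benefit is a tighter estimate and agreement with SAP 10.4.18, not power.

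**What to change.** Before database lock and unblinding, add continuous baseline T/W score to SAP 10.3.1 and 10.4.4, and continuous baseline hemoglobin to SAP 10.3.2 and 10.4.3, alongside treatment and the stratification factors. Align Protocol 9.6.2.1, 9.6.2.2, 9.6.3.3 and 9.6.3.4, and repair the broken sentences in the first two. If the omission is intended, one sentence giving the reason would settle the matter.

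No new data or patients are needed. SAP 8.2 already has "Baseline NTDT-PRO T/W Score (calculated over 7 days prior to Dose 1 Day 1 detailed in Section 18.3.1) summarized as continuous variable", and treats baseline hemoglobin likewise. The statistical cost is one degree of freedom per model. The procedural cost is a blinded SAP revision and whatever route the protocol wording requires under Protocol 13.5.

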10.4 Analyses of Other Secondary Efficacy Endpoints

The analyses of other secondary efficacy endpoints will be performed on the ITT population except for the FACIT-F and SF-36 endpoints listed in this section. The analyses of NTDT-PRO, FACIT-F, and SF-36 endpoints will be conducted based on the Health Related QoL evaluable population (Section 5.2.4).

10.4.1 FACIT-F Fatigue Subscale (FS): Mean Change from Baseline between Weeks 13 to 24 and Weeks 37 to 48

Mean FACIT-F FS score change from baseline over a 12-week interval between Weeks 13 to 24 (nominal Dose 5 to Dose 9) will be analyzed using ANCOVA method with treatment group, randomization stratification factor(s) in the model and baseline FACIT-F FS score as covariate. The baseline of FACIT-F FS is the score from the last visit prior to or on Dose 1 Day 1.

Mean change from baseline for Weeks 37 to 48 (nominal Dose 13 to Dose 17) will be analyzed similarly.

The subgroup analyses for Weeks 13-24 will be performed as described in Section 10.5.

10.4.2 NTDT-PRO SoB Score: Mean Change from Baseline between Weeks 13 to 24 and Weeks 37 to 48

Mean NTDT-PRO SoB score change from baseline over a 12-week interval between Weeks 13 to 24 will be analyzed using ANCOVA method with treatment group, randomization stratification factor(s) in the model and baseline NTDT-PRO SoB score as covariate. Similar analysis will be performed for Weeks 37 to 48.

10.4.3 Hemoglobin Mean Change Between Weeks 37 to 48

Mean Hemoglobin change from baseline over 12-week interval between Weeks 37 to 48 during the treatment period will be analyzed using ANCOVA method with treatment group and randomization stratification factor(s) in the model as covariates.

Baseline hemoglobin (Hb) is the average of 2 or more Hb measurements at least 1 week apart within 4 weeks prior to Dose 1 Day 1. The Hb values within 21 days following a transfusion may be influenced by the transfusion and will be excluded from this analysis. For discontinued subjects who do not complete 24 weeks of the DBTP, Hb data will continue to be collected. For a subject, if the Hb average over Weeks 37-48 interval cannot be calculated due to missing data, the closest Hb 12-week average will be used.

10.4.4 NTDI-PRO (T/W Domain) Mean Change Between Weeks 37 to 48

Mean NTDI-PRO (T/W domain) change from baseline over a 12-week interval between Weeks 37 to 48 (nominal Dose 13 to Dose 17) will be analyzed using ANCOVA method with treatment group and randomization stratification factor(s) in the model as covariates.

The treatment-by-stratification-factor(s) interaction will be added to the ANCOVA model as a sensitivity analysis and results from this model will be compared to the primary fixed effects model (without the interaction effect). If the interaction is significant at a 2-sided 0.1-alpha level, the nature of this interaction will be inspected as to whether it is quantitative (that is, the treatment effect is consistent in direction but not in size of effect) or qualitative (the treatment is beneficial in some values of the stratification factor(s)). If the interaction effect is found to be quantitative, results from the primary fixed effect model will be presented. If the interaction effect is found to be qualitative, further inspection will be used to identify in what values of the stratification factor(s) the treatment is more beneficial.

10.4.5 FACIT-F Fatigue Subscale (FS) Response at Weeks 13 to 24 and Weeks 37 to 48

Proportion of subjects with an increase from baseline ≥ 3 in mean FACIT-F FS score, over Weeks 13 to 24 in the luspatercept group will be compared with the placebo group. The CMH test will be used with baseline FACIT-F FS category ≥ 37 versus < 37 as the stratum to compare the response rates between the 2 groups. The selection of 37 as a threshold is based on a Phase 2 Luspatercept study (A536-06) in which it corresponds to a NTDI-PRO T/W domain scores of 4. The corresponding 95% confidence interval for odds ratio will also be provided. Similar analysis will be performed for Weeks 37 to 48.

10.4.6 SF-36 v2: Mean Change from Baseline at Week 24 and Week 48

The SF-36 Version 2.0 (acute condition with 1-week recall period) is a self-administered instrument consisting of 8 multi-item scales that assess 8 health domains: Physical functioning (PF), Role-Physical (RP), Bodily Pain (BP), General Health (GH), Vitality (VT), Social functioning (SF), Role-Emotional (RE), and Mental Health (MH). Two overall summary scores, Physical Component Summary (PCS) and Mental Component Summary (MCS), will be calculated from the 8 health domains. The primary interests of the SF-36 are the PCS and MCS norm-based scores.

Scores for each domain and composite summary scale of the SF-36 will be derived using the Quality Metric's Health Outcomes™ Scoring Software 5.1, a software designed to provide standardized scoring methods for the SF-36 based on the 2009 US general population normative data (*Maruish, 2011*). The scoring algorithm, using the 1998 US general population normative data as an example, for the SF-36 is shown in Appendix 18.3.3.

Summary statistics (n, mean, median, SD, range) for PCS and MCS norm-based scores along with the change from baseline will be summarized at Weeks 12, 24, 36, and 48 for each treatment group. The Norm-base scores will be used for domain analysis and the PCS analysis. The raw scores for each individual question and the calculated domain and component scores will be presented in the listings for SF-36.

A mixed effect repeated measure model will be used with intercept and time as the random effect. The model includes the change from baseline scores up to Week 48 as the outcome, and treatment group assignment, time (weeks since Dose 1 Day 1), baseline scores, randomization stratification factor(s), time-by-baseline score, and time-by-treatment group assignment terms in the model. The unstructured covariance matrix will be used to obtain the random effects variance components.

If the MMRM model using an unstructured covariance matrix fails to converge with the default Newton-Raphson algorithm, the Fisher scoring algorithm or another appropriate method will be used to provide initial values of the covariance parameters. In the rare event that none of the above methods yields convergence, a structured covariance, such as heterogeneous Toeplitz and Toeplitz structures, will be used to model the correlation among repeated measurements. In this case, the empirical option will be used because the sandwich variance-covariance estimator is asymptotically consistent.

To assess the extent of missing data at each assessment visit by treatment group, compliance rates for the SF-36 will be estimated on the ITT population separately based on the number of subjects included in the ITT population per treatment group who are eligible for assessment at a given scheduled visit. Subjects will be considered compliant with completion of the SF-36 assessment if at least half of the 36 items (i.e., ≥ 18 items) are completed.

Additional details of the highlighted analyses as well as sensitivity analyses, and additional analyses to assess subgroups and treatment effects on HRQoL are provided in a separate HRQoL statistical analysis plan, which will be finalized prior to database lock. The HRQoL statistical analysis plan will be appended to the separate specific HRQoL report.

